- Requirement for an increase in fraction of inspired oxygen requirements 0.20 or greater, lasting longer than 30 minutes (e.g. from 0.21 to 0.41)
- Need for intubation in a previously non-intubated subject, or unplanned use of extracorporeal membrane oxygenation (ECMO)

Note that transient fluctuations in hemodynamic and/or respiratory function may be common during thrombectomy and thrombolysis procedures, and events not meeting both severity and duration requirements are not considered meeting the definition of Clinical Deterioration. Such changes may resolve spontaneously upon continuation of an existing treatment plan, and as such are unremarkable. Vagal episodes are also, in themselves, not considered Clinical Deterioration. Shorter term changes in hemodynamic or respiratory function, when accompanied by an unplanned escalation of therapeutic measures under the primary clinician's judgement to avoid overt deterioration, may be considered Bailout Therapy. Any such escalations of therapy will be documented in detail and adjudicated by a Clinical Events Committee (CEC).

Bailout Therapy is an unplanned escalation of therapeutic measures, taken when the patient's condition has not improved or is not improving according to expectations. Potential Bailout Therapy events will be adjudicated by a Clinical Events Committee, including when any of the following occur:

- Unplanned use of additional mechanical, pharmacomechanical, pharmacologic catheter-based therapies, or systemic thrombolytics, or changing from the assigned treatment strategy, after initial treatment strategy as assigned was initiated.
 - If catheter-directed thrombolysis (CDT) was the assigned treatment strategy and emergent/clinically driven systemic thrombolytic administration (e.g. ≥ 10 mg tPA) was required after CDT was initiated, this would be considered a bailout.
 - If the length of thrombolytic administration is simply extended and is not emergent or clinically driven, this would not qualify as a bailout.
 - If mechanical thrombectomy was the assigned treatment strategy, low-dose catheter-directed **adjunctive** thrombolytic therapy (less than 10 mg tPA) that is administered intra-procedurally or post-procedurally will be *strongly discouraged* but not considered a bailout
- Surgical thrombectomy

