The initial catheter-based intervention for acute PE is considered the Index Procedure. The procedure is conducted under fluoroscopic/angiographic guidance. Refer to the Instructions for Use (IFU) for techniques and methods for device deployment. The following assessments are collected during the index procedure including:

- Anticoagulation regimen
- Clinical labs (Hemoglobin, ACT, and PTT collected just prior to index procedure intervention)
- Oxygenation status collected just prior to index procedure
- Invasive PA pressures (**required** pre-index procedure)
 - Interventionalists will collect pulmonary artery pressures immediately before primary therapeutic catheter insertion.
- Invasive PA pressures (**optional** post-index procedure)
 - Trained interventionalists will collect pulmonary artery pressures at least 10 minutes after primary therapeutic catheter (for CDT) begins therapy, or after the primary therapeutic catheter (for FlowTriever) is removed for the last time. Additional PA pressures are requested to be collected in the CDT subjects 6 hours (\pm 2 hours) post procedure using the same technique.
- Bleeding measures
- Adverse event assessment

The Index Procedure begins when access for treatment is obtained. The Index Procedure is considered complete upon exit from the procedure room. The time of exit from the procedure room is the time reference used for the subsequent visit windows including the 24-hour visit. The 7-day maximum for in-hospital primary endpoint

assessment is defined as 168 hours from the end of the Index Procedure. The 30-day Visit window refers to 30 calendar days from the day the Index Procedure ends.

Recommendations for Anticoagulation Management and Thrombolytic Therapy

In order to approximate real-world practice, the use of pre-procedure, intra-procedure, and post-procedure anticoagulation should be guided by investigator discretion, local standard of care, and in accordance with IFU for the assigned therapy.

Similarly, dose and duration of thrombolytic agents in subjects assigned to CDT is guided by investigator discretion, local standard of care, and in accordance with IFU. Initial dosing strategy should be recorded in the corresponding CRF, along with any changes in dose throughout the infusion, including extended infusion times. Bolus thrombolytics that are part of initial treatment plan are not considered bailout, although bolus lytics are discouraged in subjects assigned to FlowTriever therapy.

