- Recurrent protocol deviations or other non-compliances
- Inaccurate, incomplete, and/or untimely data recording on a recurrent basis

- Lack of cooperation with monitoring visits (e.g., failure to adequately prepare for visits, address action items from one visit to the next, or provide access to medical records)

DATA HANDLING AND RECORDKEEPING

Completing, Signing and Archiving Case Report Forms

Clinical study data will be collected using electronic case report forms (eCRFs). A web-based electronic data capture (EDC) database will be used to record and manage study data. eCRF completion guidelines and instructions for electronic data-entry will be developed in conjunction with the Sponsor and/or EDC vendor. All eCRFs must be kept in good order and updated so they always reflect the latest observations on the subjects participating in the study.

The Investigator will sign the appropriate eCRF pages and source documentation. Pertinent eCRF corrections will be made electronically and signed electronically by the Investigator. An embedded audit trail will capture the date, time, and user making entries and changes to the electronic data.

It is important to have proper data collection in a timely manner (approximately 5 business days of the study visit/assessment). When the Sponsor or designee requests additional data or clarification of data for the eCRF, the request must be answered satisfactorily in a timely manner.

Data Management and Archiving

The Sponsor and/or designee will be responsible for the processing and quality control of the data. All CRFs, copies of protocols and protocol amendments, correspondence, subject identification lists, informed consent forms, and other essential documents must be retained for a minimum of 10 years post study completion or 10 years after the last FlowTriever system or CDT system has been placed on the market (whichever is longer).

No study document or image will be destroyed without prior written agreement between the Sponsor and the Investigator prior to the conclusion of the retention period. Should the Investigator wish to assign the study records to another party or move them to another location, advance written notice must be given to the Sponsor.

Direct Access to Source Data/Documentation

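### Part of tier 4 depends on whether a therapy was planned, but the protocol does not require the plan to be recorded before treatment

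*Protocol*

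**What the plan says.** Protocol section 5 (repeated in section 17) makes intent the test: "Bailout Therapy is an unplanned escalation of therapeutic measures". The first listed trigger for adjudication is "Unplanned use of additional mechanical, pharmacomechanical, pharmacologic catheter-based therapies, or systemic thrombolytics", together with a change from the assigned strategy once it has begun. Surgical thrombectomy is a separate trigger.

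Section 5 also states what is not a bailout. An infusion that is merely extended, without an emergent or clinical reason, does not count. Nor does adjunctive catheter-directed lytic below 10 mg tPA in the thrombectomy arm. Section 7, under the recommendations on anticoagulation and thrombolytic therapy, adds a further exemption: "Bolus thrombolytics that are part of initial treatment plan are not considered bailout". The same sentence discourages boluses in FlowTriever subjects, so it covers both arms.

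On recording, the same part of section 7 says, in a paragraph about CDT subjects: "Initial dosing strategy should be recorded in the corresponding CRF, along with any changes in dose throughout the infusion, including extended infusion times". It leaves dose and duration to the investigator and local standard, in line with the IFU. Neither the Schedule of Assessments nor the baseline list contains a treatment-plan item. Section 12 expects CRF data about 5 business days after the visit or assessment.

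SAP section 2 describes the trial as open-label. Section 9 of the protocol gives the CEC site-reported data to adjudicate, under a charter that is not part of these documents.

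**The concern.** Whether a bolus, a further infusion or an additional catheter therapy was planned is a fact about intent before treatment. Nothing in the documents requires that intent to be captured before treatment. The person who later describes it knows both the arm and how the patient responded.

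The label has consequences. An unplanned escalation is a tier-4 event if the CEC accepts it. If the CEC rejects it, section 5 makes it a protocol deviation, which SAP section 3.2 lists among possible reasons for leaving the Per Protocol population. A therapy accepted as planned is neither. The label feeds the five-tier primary, the four-component secondary win ratio and the deterioration/bailout secondary endpoint. A missing record of prior intent cannot be recreated at analysis.

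**Working it through.** **1. Which parts of tier 4 depend on the plan**

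| Element | Depends on prior intent? |
|---|---|
| Bolus thrombolytic | Yes (section 7 exemption) |
| Added infusion or added catheter therapy | Yes (unplanned use, section 5) |
| Change from the assigned strategy | No; the assignment is issued in the EDC |
| Surgical thrombectomy | No |
| Adjunctive lytic under 10 mg, thrombectomy arm | No; exempt by dose |
| Hemodynamic or respiratory deterioration | No; objective criteria |

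**2. Is the plan fixed before treatment?** Section 7 sets no time for recording the CDT strategy relative to the procedure, and section 12 allows entry afterwards. No entry is asked for in FlowTriever. Section 12 also says: "An embedded audit trail will capture the date, time, and user making entries and changes to the electronic data". That dates the data entry, not the decision. Late recording is thus permitted by silence; no sentence says it outright.

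**3. Size.** The plan's own figure is 432 subjects (216 per arm) for 80% power at one-sided 0.025. It cannot be reproduced, because neither document gives the component rates or the ICU distribution. What follows uses assumed rates with no true difference: death 1%, ICH 0.5%, major bleeding 5%, tier 4 at q = 5%; ICU none / 0-24 h / over 24 h at 45/30/25; independent tiers; n = 275 per arm.

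Let a share d of FlowTriever subjects be moved out of tier 4. The other tiers yield equal wins and losses. Among pairs tied on tiers 1-3, wins minus losses at tier 4 equal (1-q+d)q - (q-d)(1-q) = d.

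- P(tie on tiers 1-3) = (0.01² + 0.99²)(0.005² + 0.995²)(0.05² + 0.95²) = 0.9802 × 0.99005 × 0.905 = 0.878.
- Net win difference Δ = 0.878 d.
- Under the null, the Finkelstein-Schoenfeld variance gives SE(Δ) = √[2/(3n) × (1 - Σπ³)], with π the probabilities of the distinct outcome profiles. Here 1 - Σπ³ = 0.906, so SE = √(2/825 × 0.906) = 0.0469.
- Type I error ≈ P(Z > 1.96 - Δ/SE).

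The simulated column is the range from runs of the protocol's statistic with 10,000 or 20,000 replicates and ICU splits 45/30/25, 30/40/30 and 60/20/20. With d = 0 they returned 2.5-2.6%.

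| d | Δ | Δ/SE | Approximation | Simulated | Same d moved in CDT instead (approximation) |
|---|---|---|---|---|---|
| 1 point | 0.0088 | 0.19 | 3.8% | 3.8-4.1% | 1.6% |
| 2 points | 0.0176 | 0.37 | 5.6% | 5.5-6.3% | 1.0% |
| 3 points | 0.0263 | 0.56 | 8.1% | 8.0-8.8% | 0.6% |

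One point is 275 × 0.01 = 2.75 subjects. Out of 275 × 0.05 = 13.75 expected tier-4 subjects, 1 to 3 points is 20% to 60%.

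**4. Sensitivity to the assumptions.** With ICU splits 30/30/40 and 5/35/60, and 216 or 275 per arm:

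- Tier-4 rate 5%: relabelling a quarter of FlowTriever tier-4 events gave 3.7-4.4%, and half gave 6.2-7.3%.
- Tier-4 rate 10%: the same fractions gave 6.0-7.0% and 12.2-17.5%.

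For the four-component secondary, which has no ICU tier to dilute the effect, shifts of 1, 2 and 3 points at the 5% rate gave about 5-6%, 10% and 18% at one-sided 0.025 (275 per arm).

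**The case against.** The strongest reply is that the CEC, not the operator, decides. Section 5 has escalations documented in detail, with reasons entered in the CRF. Section 9 calls for source documents such as operative reports and progress notes, and section 12 gives the sponsor and auditors direct access to source. A contemporaneous note may therefore show what was intended, and the unseen charter may say how the CEC uses it. This stands, and it rules out the inference a reader might draw that the operator can simply turn an endpoint event into a non-event, or that the CEC has nothing but a later description. What remains is that no provision guarantees a pre-treatment statement of the plan or says that the CEC receives one.

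A reader might also take section 7 to exempt anything that was planned. It exempts boluses only; infusions and devices come in through the word unplanned in section 5. Nor does the whole of tier 4 turn on the plan, as the first table shows.

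The direction is open as well. Boluses are discouraged in FlowTriever and low-dose adjunctive lytic is already exempt there, so intent-based exemptions may have more scope in CDT, where relabelling works against FlowTriever. The type I error figures assume relabelling in one arm only and let it remove 20-60% of all its tier-4 events, including deterioration that cannot be relabelled. They are illustrations on the upper side, not estimates.

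**Conclusion.** The gap is real and limited. For boluses, added infusions and added catheter therapies, the protocol relies on prior intent without requiring it to be recorded before treatment in either arm, in a trial where the site knows the arm. The CEC may therefore lack a pre-treatment reference for planned versus unplanned therapy.

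The documents do not show that misclassification will occur or which arm it would favor, and its size is unknown without event rates. Under the assumed rates (275 per arm, 5% tier 4, independent tiers, one-directional relabelling in FlowTriever), a shift of 1 to 3 points takes one-sided type I error from 2.5% to roughly 4-9%. The result depends mainly on how many points are moved, so a higher tier-4 rate leaves room for more. This is a worthwhile, cheap improvement rather than a flaw that invalidates the primary analysis.

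**What to change.** - **Plan entry.** In both arms, add a short EDC entry, time-stamped after assignment and before the study device enters the body. It states the site's own intended initial strategy: devices, any thrombolytic including a bolus, and any planned repeat session.
- **Use by the CEC.** Supply the entry to the CEC as the reference for what was planned. Keep the existing exemptions in sections 5 and 7. State that a plan entered or edited after device entry cannot by itself exempt a therapy.
- **No automatic event.** A therapy absent from the entry goes to CEC adjudication and does not become a tier-4 event by default. Otherwise an incomplete form could create events, mainly in CDT, where there is more to list.
- **Sensitivity analysis.** Add to the SAP a repeat of the primary analysis that counts all additional lytic or thrombus-removal therapy not on the pre-procedure entry as tier 4.

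The cost is one brief form, when the site is already in the EDC for the assignment, plus a sentence each in sections 5 and 7, the CEC charter and the SAP. Incomplete forms are the main risk, which CEC review addresses. No permitted treatment changes.

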An interim analysis of outcomes out to 30 days on the first 230 subjects was presented at the 2021 Society for Interventional Radiology Annual Conference in March, 2021, with the abstract from this conference published in the Journal of Vascular and Interventional Radiology, as well as earlier conferences.⁵⁸⁻⁶⁰ These subjects (60.7 ± 13.9 years, 52.2% male) were enrolled across 17 sites, with 93.0% having intermediate-risk PE and 7.0% high-risk PE. The average baseline RV/LV ratio was 1.6 ± 0.5 and sPESI was 1.6 ± 1.1 . 96.3% of subjects had elevated biomarkers, and 69.7% of subjects had concomitant DVT. The primary endpoint of composite MAEs occurred in three (1.3%) subjects, all of which were non-ICH major bleeds, and no deaths occurred within 48 hours.

In-hospital outcomes demonstrated significant improvements across several acute parameters. Subjects experienced significant on-table hemodynamic improvements, including a 21.9% decrease in mean pulmonary artery pressure (32.0 mmHg to 25.0 mmHg, $P < 0.0001$) and a 20.1% decrease in heart rate (pre-procedural high of 113.2 bpm to 90.5 bpm immediately post-procedure, $P < 0.0001$). There was only one (0.4%) access site complication. The median post-procedure hospital length of stay was 3.0 [2.0 – 5.1] days and ICU length of stay was 0.0 [0.0 – 1.1] days.

30-day follow up data was available for 201 subjects in this analysis. In this population, there was one death (0.5% mortality), which was unrelated to the device, and there were ten hospital readmissions, one of which was related to the procedure. The average RV/LV ratio improved by 33.2% at a median follow up of 30 days ($P < 0.0001$) and subjects with confirmed baseline dyspnea had a significant improvement from baseline to 30 days (Modified Medical Research Council Dyspnea Scale, 3.0 ± 1.0 to 1.4 ± 1.3 , $P < 0.0001$).

These results of the FLASH all-comer registry demonstrate both safety and efficacy of the FlowTriever System, with a low all-cause mortality rate (0.0% at 48 hours, 0.5% at 30 days; no device-related deaths), along with significant and immediate hemodynamic improvements and continued improvements in RV/LV ratio and dyspnea out to 30 days.

FLAME Study Design and Status

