^f Imaging can be either echo or CT, but needs to be the same modality within each patient at Baseline and 24-hour visit

^g Note that the evaluation of endpoint considerations include All-cause mortality, ICH, Major bleeding, Clinical deterioration and/or escalation to a bailout therapy, and ICU admission and ICU length-of-stay. These are assessed at hospital discharge or 7 days after the index procedure, whichever is earlier. If a subject is still in the hospital and exits the study for any reason before the 30-day Visit, evaluation of primary endpoint components should be completed at the time of patient exit.

^h The Index Procedure begins when access for treatment is obtained. The Index Procedure is considered complete upon exit from the procedure room. The time of exit from the procedure room is the time reference used for the subsequent visit windows including the 24-hour visit.

BASELINE ASSESSMENTS

The baseline assessments must be done \leq 72 hours of Index Procedure including:

- Informed consent
- Inclusion/exclusion review
- Demographics
- Medical history, risk factors, and PE condition
- Anticoagulation regimen
- Clinical labs (Hemoglobin, Troponin)
- Cardiac imaging (Echo or CT)
 - Imaging can be either echo or CT, but needs to be the same modality within each patient at baseline and 24-hour visit.
- mMRC dyspnea score, Borg, and NYHA

ALLOCATION AND RANDOMIZATION

Upon the patient meeting baseline eligibility criteria and providing informed consent, a check against the list of absolute contraindications to thrombolytics is performed (see Figure 9: Patient Enrollment Flowchart). Subjects with one or more absolute contraindications to thrombolytics and whose initial treatment plan includes FlowTriever are allocated to the Contraindication Cohort. Subjects without any absolute contraindications (whether there are relative contraindications to thrombolytics or no contraindication to thrombolytics) are allocated to the RCT Cohort.

Study sites will receive the subject randomization assignment electronically in the electronic data capture (EDC) system upon completion of baseline information used to stratify randomization using the calculated VTE-BLEED score. Subjects will be randomized to and treated with (a) mechanical thrombectomy with FlowTriever or (b) catheter-directed thrombolysis per local practice standards.

INDEX PROCEDURE

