Participation is completely voluntary, and each subject is free to withdraw consent to participate in the study at any time. An investigator also has the right to withdraw the subject from the study for reasons concerning the health or well-being of the subject, or in the case of lack of cooperation. Should a subject decide to withdraw consent for any reason, or should the investigator decide to withdraw the subject, all efforts will be made to complete and report the observations up to the time of withdrawal as thoroughly as possible. A complete final evaluation at the time of the subject's withdrawal must be made and an explanation given as to why the subject is withdrawing or being withdrawn from the study.

The reason for, and date of, withdrawal must be recorded on the subject's Study Exit CRF. If the reason for the withdrawal is a device, drug, or procedure-related AE, the event must be reported to the Sponsor and recorded in the CRF.

If the index catheter-based intervention procedure is aborted before treatment catheter insertion or is not performed, the subject is considered a screen fail.

All efforts will be made to return subjects for all follow up visits. Due diligence in reaching the subject must be made by two documented telephone contact attempts, emails, or regular postal mail letters. After the above attempts are made, if no response from the subject or their designated caregiver is obtained, the final evaluation of the subject and study exit will be dated on the last visit at which study-related assessments were performed. The Study Exit CRF page will be completed, and communication attempts will be documented.

COVID-19 EFFECT ON RESEARCH

This study was designed to compare the clinical outcomes of patients treated with the FlowTriever System versus Catheter-Directed Thrombolysis (CDT) for use in acute pulmonary embolism (PE). As a result of the COVID-19 pandemic, clinical practice patterns may be affected, and subject visits may be postponed or eliminated. Additionally, subjects may not be willing to be seen by their provider potentially exposing both parties to the virus. In order to protect subject and provider safety, some data may be collected from subjects over the phone if allowed by the IRB/EC.

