9. SAFETY ASSESSMENT

DEFINING ADVERSE EVENTS

An Adverse Event (AE) is an untoward medical occurrence, unintended disease or injury, or untoward clinical signs (including abnormal laboratory findings) in *subjects*, users or other persons, whether or not related to the *investigational* medical device* and whether anticipated or unanticipated (ISO 14155:2020, 3.2).

*NOTE 1: All medical devices in the context of this clinical trial are considered investigational devices.

NOTE 2: This adverse event definition includes events related to the procedures involved.

Disease signs and symptoms that existed prior to study participation are not considered AEs unless the disease or condition recurs after the subject has recovered from pre-existing condition, or the disease or condition worsens in intensity or frequency during the study.

Collection of adverse events will start after point of enrollment. Adverse events will be monitored throughout the study. Investigators must obtain all information available to determine the causality and outcome of the AE and to assess whether it meets the criteria for classification as a serious adverse event (SAE) requiring immediate notification to the sponsor or its designated representative. All reported AEs will be documented on the appropriate CRF and will include the event description (sign, symptom, or diagnosis), timing of onset and resolution, seriousness, severity, cause, and action taken. The investigator must assess causality and severity for all AEs.

All AEs will be followed by the Investigator until resolution or until the 30 Day follow up visit is completed or until study exit. When the study subject's participation in PEERLESS has ended, after the 30-Day follow-up visit or in case of patient withdrawal, the patient will continue to be treated and followed-up as per the hospital's standard of care.

DEFINING ADVERSE DEVICE EFFECT (ADE)

An Adverse Device Effect (ADE) is an AE related to the use of an investigational medical device.

NOTE 1: This definition includes AEs resulting from insufficient or inadequate instructions for use, deployment, implantation, installation, or operation, or any malfunction of the investigational medical device.

NOTE 2: This definition includes any event resulting from an error use or from intentional misuse of the investigational medical device.

NOTE 3: This includes 'comparator' if the comparator is a medical device. (ISO 14155:2020, 3.1)

DEFINING SERIOUS ADVERSE EVENT (SAE)

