10. STATISTICS & DATA ANALYSIS

SAMPLE SIZE

By assuming an 80% power with one-sided alpha of 2.5%, the win ratio methodology is applied to the primary endpoint that consists of five components. The required sample size is 432 subjects (216 subjects per arm); and planning for follow up attrition and further describing secondary endpoints/exploratory analysis, the study will enroll up to a total of 550 randomized subjects (RCT Cohort). The sample size assumptions are based on Inari sponsored studies and a review of literature.

Up to 150 additional subjects who meet all eligibility criteria and who have an absolute contraindication to thrombolytics, whose initial planned primary treatment strategy includes FlowTriever, will be enrolled as part of the Contraindication Cohort. The same clinical assessments and follow up schedule will be administered in this cohort as is described for the RCT Cohort. The Contraindication cohort data will not be used for any PEERLESS protocol-defined hypothesis testing nor used to calculate any primary or secondary endpoints.

STATISTICAL METHODOLOGY

The statistical design objective for this trial is to compare the clinical outcomes of the FlowTriever System versus Catheter-Directed Thrombolysis (CDT) for use in the treatment of acute pulmonary embolism (PE). Since the primary endpoint is a composite clinical endpoint, a modified generalized Wilcoxon test (F-S test) proposed by Finkelstein & Schoenfeld⁷³ will be applied to examine the performance differences between the two treatment arms.

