3.3. Contraindication Cohort

Up to 150 additional subjects who meet study eligibility criteria and who have an absolute contraindication to thrombolytics, whose initial planned primary treatment strategy includes FlowTriever, will be evaluated as part of the Contraindication Cohort. The same RCT Cohort clinical assessments and follow up schedule will be administered in the Contraindication Cohort.

4. Incomplete Date Handling and Missing Data

Partial date/time input will not be collected in the electronic case report form (eCRF), i.e., date/time will be either non-missing or completely missing. On a case-by-case basis, when the missing date/time imputation is required, the most conservative date/time will be used.

In general, main analysis will be conducted in the complete case analysis. Additional sensitivity analysis will be conducted by imputing missing data using multiple imputation.

PROPRIETARY AND CONFIDENTIAL

The information contained in this document is the sole property of Inari Medical

	PEERLESS Study: Statistical Analysis Plan	Version 5.0 March 22, 2024 Page 15 of 25
---	--	--

5. Statistical Methods and Analysis

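### Observation for the 30-day safety endpoints stops at investigator withdrawal or after two failed contact attempts, and no vital-status check is required before the subject is closed out

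*Protocol*

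**What the plan says.** **Investigator withdrawal.** Protocol section 7, Withdrawals and Lost to Follow Up, states: "An investigator also has the right to withdraw the subject from the study for reasons concerning the health or well-being of the subject". Non-cooperation is a second ground. After withdrawal, the section asks for observations only up to that time. It also requires a complete final evaluation, a recorded reason and date, and a report to the sponsor if an event related to device, drug or procedure was the cause.

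**Unreachable subjects.** Two documented attempts by telephone, email or post are enough. If neither the subject nor a designated caregiver responds, "the final evaluation of the subject and study exit will be dated on the last visit at which study-related assessments were performed".

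**Adverse events.** Protocol section 9, Defining Adverse Events: "All AEs will be followed by the Investigator until resolution or until the 30 Day follow up visit is completed or until study exit".

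**Exit while in hospital.** Note g to the Schedule of Assessments, repeated under the discharge and 30-day visits, begins "If a subject is still in the hospital and exits the study for any reason before the 30-day Visit, evaluation of primary endpoint" and goes on to have the components completed at the time of exit. The primary window itself runs to discharge or 168 hours, whichever is sooner.

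**Analysis.** SAP section 4 says that, in general, the "main analysis will be conducted in the complete case analysis", with multiple imputation as an additional sensitivity analysis. SAP 5.4.3 tests 30-day all-cause mortality with Fisher's exact test against a one-sided alternative. SAP 5.6 lists 30-day mortality, 30-day readmission and device- or drug-related SAEs as safety endpoints, with alpha 0.05.

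**The concern.** The allocated treatment is a single catheter procedure, with an infusion in the CDT arm. Later visits only collect assessments. Once treatment has been given, withdrawing a subject from the study for health reasons mainly ends data collection. The trial is open-label, so the person deciding knows the arm.

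The loss-to-follow-up rule has a similar effect. If a patient dies at home after discharge and nobody answers two messages, the file closes at the discharge visit with 30-day status unknown. No passage sends the site to the hospital record, the treating physician or a death record. The protocol requests death certificates and autopsy reports, but only for deaths the site already knows about. The Clinical Events Committee works from site-reported data and cannot adjudicate a death that was never reported.

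At stake are the three 30-day safety endpoints. Deaths are likely to be few, so one or two lost deaths could change the picture. If death is the reason for silence, imputation from observed subjects will generally not recover it. The SAP states neither the imputation model nor its missing-data assumption.

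**Working it through.** **Figures in the plan.** The withdrawal rules carry no figure. The only number bearing on attrition is the rise from 432 required to 550 enrolled. The 432 cannot be reproduced because the component event rates are not given. The cushion is 1 − 432/550 = 21.5%, but it also serves secondary and exploratory description, so it is not a loss rate.

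**Inputs.**
- 275 per arm: 550 at 1:1 (Protocol section 6).
- Registry follow-up (Protocol section 3, FLASH Interim Results): "30-day follow up data was available for 201 subjects in this analysis", out of 230. Without data: 29/230 = 12.6%. Enrolment was ongoing, so some subjects may not yet have reached day 30. This is an upper, illustrative figure.
- Registry 30-day mortality: 1/201 = 0.5%.
- Assumed, not in the documents: unknown status as low as 2% or 5%, and mortality among unknowns of 0.5% to 10%.

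**Step 1: unknowns against deaths.** 275 × 2% = 5.5, about 6. 275 × 12.6% = 34.7, about 35. Expected deaths at 0.5%: 275 × 0.005 = 1.4 per arm. At an assumed 3%: 275 × 0.03 = 8.3. The unknowns could outnumber the deaths.

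**Step 2: bias in the complete-case rate.** With m unknown per arm and mortality q among them, true mortality = [(275 − m) × 0.005 + m × q] / 275. Complete-case analysis shows 0.50% throughout.

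| Unknown per arm | q = 0.5% | q = 2% | q = 5% | q = 10% |
|---|---|---|---|---|
| 6 (2%) | 0.50% | 0.53% | 0.60% | 0.71% |
| 14 (5%) | 0.50% | 0.58% | 0.73% | 0.98% |
| 35 (12.6%) | 0.50% | 0.69% | 1.07% | 1.71% |

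If unknowns die at the same rate as the rest, there is no bias. At 12.6% unknown with 5% mortality among them, the true rate is 1.07/0.50 = 2.1 times the reported one.

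**Step 3: sensitivity of the planned test.** One-sided Fisher, alternative of lower mortality with FlowTriever, 275 per arm:
- 0 vs 5 deaths: p = (275·274·273·272·271)/(550·549·548·547·546) = 0.031. This is the smallest split that reaches 0.05.
- 1 vs 5 deaths: P(0) = 0.0307 × 270/545 = 0.0152; P(1) = 0.0152 × 275/45 = 0.0929; p = 0.108.
- With 5 or 35 FlowTriever subjects dropped as unknown, the complete-case result would be 0/270 vs 5/275 (p = 0.032) or 0/240 vs 5/275 (p = 0.043). Both are below 0.05, although one hidden FlowTriever death restores p = 0.108.
- A missed CDT death works the other way: 0 vs 4 gives (275·274·273·272)/(550·549·548·547) = 0.062, against 0.031 for the true 0 vs 5.

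These p-values are set against 0.05 read as one-sided. SAP 5.6 does not state the sidedness of the safety alpha. The two-sided p for 0 vs 5 is 0.061.

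**Step 4: primary endpoint.** A subject still in the ICU who exits the study at hour 20 is evaluated at exit. The stay could be scored in the 0–24 hour category when the full record would show more than 24 hours, which ranks worse in the hierarchy. No rule covers the unobserved part of the window.

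**The case against.** The protocol has more safeguards than the two rules suggest. A full final evaluation is mandatory at withdrawal, and a related event that causes withdrawal must be reported, so harm before exit should be captured. All efforts are to be made to bring subjects back, and 30-day visits may be remote where the IRB/EC allows. A caregiver who answers can report a death, and two attempts are a minimum. Multiple imputation is planned as a sensitivity analysis. All of this stands, and it confines the gap to harm after exit, chiefly where no contact responds or the investigator has withdrawn the subject.

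A reader might infer that the rules remove the patients most likely to have been harmed, or remove more from one arm. The documents do not support that: they give no withdrawal rates or reasons by arm, and non-cooperation is also a ground. Differential loss is possible but not shown.

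A reader might also build a more dramatic example: 4 vs 4 known deaths, then 9 hidden deaths in one arm, giving 13 vs 4 and a two-sided p of 0.046. Even with 35 unknowns this needs 9/35 = 26% mortality among them, and with 6 unknowns it is impossible. It also uses a two-sided test where SAP 5.4.3 sets a one-sided alternative.

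Finally, the investigator's right to withdraw a subject protects that subject, and removing it would be hard to defend. Continued passive follow-up achieves the aim without doing so.

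**Conclusion.** The concern holds for the 30-day safety endpoints. Followed as written, the plan allows a death after exit to be recorded as loss to follow-up and to leave the main 30-day mortality test. The same gap affects readmission and related SAEs.

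The size is unknown. With 2% to 12.6% unknown and 2% to 10% mortality among them, true 30-day mortality would be 0.53% to 1.71% where complete cases show 0.50%. These are assumed ranges, not trial data. The shift from p = 0.031 to p = 0.108 shows how fragile a test on so few deaths is. It does not predict a result.

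A reader might infer that the primary endpoint is compromised too. The documents support only a narrow point: it is assessed in hospital, capped at 168 hours and evaluated at exit, so only subjects who leave the study while still inpatients are exposed. Nothing suggests that they are many. No figure in the plan is overturned. The change should be made because it is cheap and closes a real gap in a named safety endpoint.

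**What to change.** 1. Before a subject is closed as lost, require a vital-status check at day 30 or later from the hospital record, treating physician, designated contact or public death record, where consent and local law allow. Record the status and its date.
2. Keep the investigator's right to withdraw a subject, but separate it from withdrawal of consent. After investigator withdrawal, continue chart-based collection of 30-day vital status, readmission and SAEs unless the subject refuses.
3. Reconcile note g with the discharge/168-hour window. For subjects who exit while in hospital, complete the primary components, including ICU stay, from the hospital record where consent allows.

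Cost: a protocol amendment, a consent-form sentence covering record and vital-status checks, an eCRF field, and small site effort for what should be a few subjects. No visits or procedures are added. Sites hold the identification lists, so the checks would fall to them under local privacy rules in the US, UK and Europe. Where consent is withdrawn or the law forbids a check, status stays unknown and should be reported as such by arm.
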